3 STUDY IMPLEMENTATION

3.1 STUDY DESIGN

This is an open label Phase I/II trial which consists of safety run-in phases IA and IB and an expansion phase II.

During the safety run-in phase IA, the safety and recommended Phase IB dose of M7824 in combination with M9241 will be determined in Cohort 1 ([Schema 1](#)).

During safety run-in phase IB the safety and recommended Phase II dose (RP2D) of M7824 in combination with M9241 and SBRT will be determined in Cohort 2 ([Schema 2](#)).

During Phase II, when RP2D of M7824 and M9241 in combination with SBRT is estimated, we will proceed with enrollment to Cohort 3 to evaluate efficacy of the M7824 and M9241 in combination with standard SBRT.

Patients will receive treatment in cycles consisting of 28 (+/- 3) days (**Note:** in Phase IA there is additional one-time infusion of M7824 at Day -14).

Administration of M7824 will be every 2 weeks by IV infusion on Days 1 and 15 of every cycle, starting on Cycle 1. (Note: in Phase IA there will be additional infusion of M7824 at Day -14).

Administration of M9241 will be every 4 weeks by subcutaneous injection on Day 1 of every cycle, starting on Cycle 1.

SBRT on this trial will be delivered per standard of care (Phase IB and Phase II), starting on Day 17 (+5 days) of Cycle 1 and continue for 5 consecutive business days (except federal holidays).

Note: This protocol will proceed to phase IB only after Radiation Safety approval of SBRT procedure, currently pending because of new SBRT guidance for pancreatic cancer.

After SBRT completion, treatment with M7824 in combination with M9241 will continue until patient meets off treatment criteria (Section [3.11.1](#)).

[figure not shown]
[figure not shown]
For patients who are benefiting from combination therapy, since we don't know which agent is driving the response (i.e. either of the drugs alone or the combination), in the event that one drug is causing toxicities and have to be discontinued, it is reasonable to continue the other drug to see if the patient might benefit from it. Since it might not be known which of the two immunology agents (M7824 or M9241) contributes to a possible positive signal, omission of one may allow a better designation for the beneficial anti-tumor effect. Based on preclinical rationale outlined in Section [1.2.3](#), there is a reasonable expectation that SBRT combined with either M9241 or M7824 may still be beneficial.

At Cycle 3 Day 15 (+/- 7 days) patient will undergo imaging and every 2 Cycles (+/-5 days) thereafter.

[figure not shown]
If during the treatment patient's tumors become resectable per standard of care, M7824 and/or M9241 will be stopped at least 5 days prior to the scheduled date of surgery. Surgery is not part of this protocol and will be done as standard of care procedure with enrollment of patient to another surgical protocol in NIH or at home institution.

If surgical exploration does not result in a successful removal of the tumor, patient will be able to return to treatment following recovery from surgery (See section 3.5.3). If tumor removed successfully, patient will be taken off protocol treatment.

Schema 1: Phase IA.

Schema 2: Phase IB

3.1.1 Dose Limiting Toxicity

The DLT period for the phase IA is 6 weeks (Day -14 to Day 28 of Cycle 1), the DLT period for the phase IB is 4 weeks (from Day 1 Cycle 1 to Day 28 Cycle 1).

Any Grade ≥ 3 adverse event (AE), occurring during the DLT evaluation period, **except** for those listed below:

- Adverse event unrelated, or unlikely related to study agents AND probably or definitely related to other causes
- Grade 3 or 4 clinically asymptomatic neutropenia if not lasting > 1 cycle (14 days) (observed on laboratory value only)
- Clinically asymptomatic grade 3 thrombocytopenia if not lasting > 1 cycle (14 days) (observed on laboratory value only with no clinically discernable bleeding events)
- Grade 3 diarrhea or skin toxicity that resolves to Grade ≤ 1 in less than 7 days after medical management (e.g., immunosuppressant treatment) has been initiated
- Tumor flare phenomenon defined as local pain, irritation, or rash localized at sites of known or suspected tumor.
- Transient (≤ 6 hours) Grade 3 flu-like symptoms or fever, which is controlled with medical management.
- Transient (≤ 24 hours) Grade 3 fatigue, local reactions, headache, nausea, emesis that resolves to \leq Grade 1 or Baseline grade.

- Any isolated and single Grade 3 liver function test abnormality in the form of transaminase, alkaline phosphatase, or bilirubin elevation with NO other associated laboratory (or other) abnormality that is not associated with symptoms or clinical manifestations of hepatitis or any immune-related event and which has resolved to Grade ≤ 1 within the subsequent cycle (14 days)
- Any isolated and single Grade 3 amylase or lipase abnormality with no other associated laboratory (or other) abnormality that is not associated with symptoms or clinical manifestations of pancreatitis and which has resolved to Grade ≤ 1 within the subsequent cycle (14 days)
- Any isolated and single Grade 3 Hgb decrease (< 8.0 g/dL) that is clinically manageable with blood transfusions or erythroid growth factor and has resolved to Grade 2 not requiring blood transfusions or erythroid growth factor therapy with the subsequent cycle (14 days).

Failure to resume SBRT after a hold of ≥ 1 week will be analyzed as a DLT within respective dose level group (Phase IB only)

3.1.2 Phase IA/IB:

Every subject of each dose level group of the phase 1 study will be observed for at least 7 days after first dose of M7824 or M7824 and M9241 before the subsequent subject can be treated.

Subjects who do not complete the DLT observation period for reasons other than a DLT will be replaced and not included in the evaluation.

The recommended phase 2 dose (RP2D) is the dose levels of M7824 and M9241 in combination with SBRT at which ≤ 1 of 6 individuals experienced a DLT during the first cycle (28 days) of combinational treatment with M7824, M9241 and SBRT.

In case of DLT, DLT will be documented and patient, per PI discretion, may continue study treatment if toxicity could be managed by interruption of the dose of study treatment or dose reductions (See Section 3.4). Patient, once having DLT, will not be used for DLT evaluation on another dose level if treated on another dose level.

SBRT

Dose modifications dosage adjustment is based upon the degree of hematologic and non-hematologic toxicity experienced by the patient at the discretion of the treating radiation oncologist. Patients will be monitored with a complete blood count (CBC), including differential and platelet count. If marrow suppression is detected, SBRT should be modified or suspended according to the standard guidelines on management of RT-associated toxicities and discretion of the treating radiation oncologist (See section 3.4.3). These subjects will be part of the DLT evaluation of the respective M7824 and M9241 dose level they were accrued to.

Failure to resume SBRT after a hold of ≥ 1 week will be analyzed as a DLT within respective dose level group. In case of DLT, attributed to SBRT, patients will be taken off SBRT treatment and per PI discretion may continue M7824 and M9241 only.

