1.2.9 Rationale for this clinical trial

The administration of M7824 and M9241 in combination with SBRT to subjects with locally advanced pancreatic cancer is justified by the following:

- The synergistic action of PD-L1 inhibition mediated by the dual PD-L1 TGFβ blocker M7824 and RT, including the emerging clinical data of improved outcome upon checkpoint blockade and RT.
- The synergistic action of M9241 and RT.
- The synergistic action of M7824 and M9241.

- Administered dose and schedule of the standard RT is not changed due to the addition of M7824 and/or M9241.
- M7824 and M9241 and RT have largely non-overlapping toxicity profiles which are manageable.

1.2.9.1 Rationale for M7824 and M9241 Dose Levels with special consideration of overlapping toxicities with SBRT

The safety run-in of M7824 and M9241 will be carried out in patients with stages III and IV or locally advanced pancreas cancer.

The toxicity profile of M7824 is predominantly benign, see section [1.2.5](#).

M7824 and SBRT carry hematological toxicities (anemia for M7824), M9241 and SBRT harbor overlaps in hematological and non-hematological GI toxicities in the form of lymphopenia as well as LFT elevations (although they were for M9241 reported as clinically not significant). While these AEs for monotherapy with M7824 and M9241 appear to be manageable and not life-threatening (predominantly grade 1 and 2 for M9241) it is not known what the side effect profile is in combination with SBRT. Thus, there is a dedicated safety run-in cohort to determine safety and tolerability of M7824 and M9241 when combined with SBRT (Phase IB part of the study).

The first 6 patients will receive M7824 at a fixed dose of 1,200 mg on day -14 followed by M7824 +M9241 combination on cycle 1 day 1.

The rationale for the starting dose of 16.8µg/kg of M9241 via subcutaneous injection every 4 weeks, which was found to be the MTD of this agent, is based on the clinical safety data of this dose in the phase I study of 59 patients conducted at the Center for Cancer Research NIH.[\[48\]](#)

Due to the transient clinically mild nature of these AEs (see section [1.2.6.1](#)) M9241 is initially combined at its MTD of 16.8µg/kg every 4 weeks dose with M7824.

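### The Phase IB DLT period and evaluability rule are tied to the first drug dose: patients are observed for only 6–11 days from the first SBRT fraction, and no rule requires that SBRT was given

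*Combined protocol and SAP*

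**What the plan says.** - **Purpose.** Section 1.2.9.1 notes that the side-effect profile with SBRT is not known, and that for this reason "there is a dedicated safety run-in cohort to determine safety and tolerability of M7824 and M9241 when combined with SBRT".
- **RP2D rule.** Section 3.1.2 accepts a dose level if at most 1 of 6 patients has a DLT in the first 28-day cycle of treatment with M7824, M9241 and SBRT together. Section 3.1.2.2 likewise describes the six as treated with all three.
- **Window.** Section 3.1.1: "the DLT period for the phase IB is 4 weeks (from Day 1 Cycle 1 to Day 28 Cycle 1". For Phase IA: "The DLT period for the phase IA is 6 weeks (Day -14 to Day 28 of Cycle 1".
- **SBRT timing.** Section 3.1 has SBRT "starting on Day 17 (+5 days) of Cycle 1 and continue for 5 consecutive business days (except federal holidays".
- **Gate to Phase II.** Section 3.1.3 opens Phase II once the RP2D is estimated and 28 days have passed since the sixth patient's first treatment.
- **Who counts.** Section 3.1.2, under a heading that covers both run-ins: "Subjects who do not complete the DLT observation period for reasons other than a DLT will be replaced and not included in the evaluation". The MTD-evaluable population in Section 10.3 repeats this and otherwise takes everyone enrolled in the run-in.
- **SBRT-specific DLT.** Sections 3.1.1 and 3.1.2 score "Failure to resume SBRT after a hold of" at least 1 week as a DLT.
- **Blocked or held SBRT.** Table 15 in Section 3.4.3 bars starting SBRT below stated granulocyte and platelet limits. The text after it says to hold SBRT for hematological toxicity and to discontinue it if the toxicity has not resolved within 2 weeks.

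**The concern.** The RP2D of the triple combination is a primary objective and rests on six patients. The rule speaks of 28 days of combined treatment, but SBRT joins only in the last part of those 28 days. A toxicity that appears after Day 28 cannot enter the six-patient count, even if SBRT ended only days before.

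Separately, no rule removes a Phase IB patient who received no SBRT. Such a patient says little about the question Phase IB asks, yet can fill one of six places as a non-DLT. Both gaps push the decision the same way, toward declaring the combination tolerable and opening Phase II.

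**Working it through.** **1. The plan's own figures.** Phase IB: Day 1 to Day 28 is 28 days, or 4 weeks. Phase IA: 14 + 28 = 42 days, or 6 weeks. Both agree with Section 3.1.1.

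**2. Observation from the first fraction.** Input: first fraction on Day *s*, with *s* from 17 to 22 (Section 3.1). Elapsed days to the end of the window = 28 − *s*.
- *s* = 17: 28 − 17 = 11 days
- *s* = 22: 28 − 22 = 6 days

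Counted the same way, the Phase IA window gives its added component (M9241, Day 1) 28 − 1 = 27 days.

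**3. Observation after the last fraction.** Assumption: Day 1 falls on a weekday, and fractions are given on five successive business days. Crossing Day 1 on Monday to Friday with weekday starts on Days 17 to 22 gives 21 feasible schedules.
- A Monday start ends at *s* + 4; any other weekday start ends at *s* + 6.
- The last fraction falls on Day 22 to 28, so 28 minus that day is 0 to 6 days (median 3). It is 0 in 4 of the 21 schedules.
- One federal holiday on any of fractions 2 to 5 moves the last fraction to *s* + 7. Of 21 × 4 = 84 placements, the 20 with *s* = 22 end on Day 29, after the window has closed.

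**4. The hold clause against the window.** A 1-week hold that begins on Day 22 is complete on Day 29, so a hold beginning on Day 22 or later cannot be scored inside the window. The 2-week limit of Section 3.4.3, counted from Day 17, ends on Day 31.

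**5. Evaluability, side by side.**
- The response and toxicity populations in Section 10.3 both name SBRT. The MTD-evaluable population does not.
- The Section 3.1.2 replacement rule acts only on patients who fail to complete the period. A patient who stays on the drugs to Day 28 completes it, with or without SBRT.
- Low counts that block a start need not be DLTs themselves. Section 3.1.1 scores grade 3 or higher events only, and exempts "Clinically asymptomatic grade 3 thrombocytopenia if not lasting" more than 14 days, with a similar exemption for asymptomatic grade 3 or 4 neutropenia.
- The SBRT-specific DLT speaks of failing to *resume*. Failing to start is not named. A start missed for reasons other than toxicity is not addressed at all.

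**6. Illustration of effect.** The documents give neither the true DLT rate nor the number of unexposed patients, so these are assumptions. With *n* exposed patients and DLT rate *p*, and unexposed patients assumed to have no DLT:

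P(pass) = (1 − *p*)^*n* + *n* *p* (1 − *p*)^(*n* − 1)

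At *p* = 1/3, the limit used in Section 10.4.4:
- six exposed: 64/729 + 192/729 = 256/729 = 0.351
- five exposed: 32/243 + 80/243 = 112/243 = 0.461

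| True DLT rate | Six exposed | Five exposed |
|---|---|---|
| 20% | 0.66 | 0.74 |
| 30% | 0.42 | 0.53 |
| 40% | 0.23 | 0.34 |

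If instead all six are exposed but a share *f* of DLTs arises after Day 28, put *p* = (1/3)(1 − *f*). For *f* = 10%, 25% and 50%, P(pass) is 0.420, 0.534 and 0.737.

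**The case against.** **The intent is clear.** The RP2D sentence and Section 3.1.2.2 both describe patients treated with all three components, and the shared evaluability rule could not require SBRT because Phase IA has none. This explains the omission. It does not supply a rule that removes an unirradiated Phase IB patient.

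**A count-blocked start may already be covered.** A reader might infer that a patient whose SBRT never starts because of low counts is bound to be scored as a non-DLT. The documents do not support that. Section 3.4.3 follows the do-not-start limits directly with the hold instruction, and Section 3.1.2 sends marrow suppression to that section and keeps those patients in the DLT evaluation. Such a start could fairly be read as a *hold* and scored as a DLT. What stands is that the DLT clause says only *resume*, so the scoring is open. Section 3.4.3 also calls low pre-treatment counts rare.

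**The window is a design choice, and there are other safeguards.** Only M9241 is de-escalated; the SBRT schedule is fixed and described as standard of care. Enrollment halts for grade 5 or repeated grade 4 toxicity (Section 3.2). AEs are recorded to 28 days after the last study agent (Section 6.1), and the SBRT completion rate is reported (Section 10.4.2). Dose-level decisions draw on earlier patients' toxicity (Section 7.4.1), and Phase II carries a cumulative DLT limit of less than 1/3 (Section 10.4.4). At 10 patients per year, entries average about 36 days apart, so patient 5 would be near Day 64 when patient 6 reaches Day 28. These are real protections. But the required spacing is only 7 days after first dose, and none of them puts an event after Day 28 into the six-patient count or replaces an unexposed patient.

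**Conclusion.** The point holds as a mismatch between the RP2D definition and the rules that implement it. Observation is 6 to 11 days from the first fraction and 0 to 6 days after the last (weekday Day 1, no holiday). A Phase IB patient who completes Day 28 without SBRT can count as a non-DLT. It should be fixed; confidence is moderate, because the intent is visible and part of the gap is a matter of reading.

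The direction is toward accepting the regimen. The size is unknown. The 46% is not an estimate: it assumes a true rate of 1/3, exactly one unexposed patient, and no drug-related DLT in that patient. Any drug-related risk would put the figure between 35% and 46%.

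A reader might also cite the series in Section 1.2.7 with a median of 6.3 months to grade 2 to 4 toxicity as proof that the window is too short. It does not serve that purpose, since no window of a few weeks would capture such events. The argument here is only that the period should observe the component being added.

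**What to change.** Reconcile Sections 3.1, 3.1.1, 3.1.2, 3.1.2.2, 3.1.3, 3.4.3 and 10.3, in this order:

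1. State whether a toxicity-related failure to start SBRT is a *hold*, and how it is scored. This comes first, so that patients blocked by toxicity are not simply replaced and their information lost.
2. For Phase IB only, count a patient without a DLT among the six only if a sponsor-defined minimum of SBRT was delivered and the observation period was completed. Otherwise replace the patient.
3. Define the Phase IB DLT period relative to SBRT delivery, the same for every patient, with the length chosen and justified by the sponsor. Tie the Phase II gate in Section 3.1.3 to the same point.

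**Cost.** This is amendment wording, and there is time for it: "This protocol will proceed to phase IB only after Radiation Safety approval of SBRT procedure". The delay depends on the length chosen. Purely as illustration, periods closing 7, 14 or 28 days after a last fraction on Day 22 to 28 would end on Day 29–35, 36–42 or 50–56, which is 1 to 28 days later per dose level than now. Each replacement costs about 12/10 = 1.2 months, or 5 weeks, at the planned accrual. Section 10.2 leaves 52 − 49 = 3 spare places, or 52 − 43 = 9 if six Phase IB patients carry into Phase II.

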3.1.2.2 Cohort 2, Phase IB, Arm 1B

6 to 12 patients will be enrolled in Arm 1B. Enrollment will start after completion of Arm 1A.

Dose de-escalation will proceed in dose levels of 6 patients.

6 subjects will be enrolled in Dose Level 0 (**Table 6**) and treated with combination of M7824, M9241 and SBRT.

If < 2 patients experience DLT during DLT period, the Dose level 0 will be the RP2D and next patients will be enrolled into Cohort 3 the phase II portion of the study.

If ≥ 2 experience a DLT at DL 0, the Dose Level 0 enrollment will be stopped, and DL -1 will be tested in 6 patients. If <2 patients experience a DLT, dose level -1 will be used as RP2D for M7824 and M9241 in combination with SBRT in the Phase II.

If ≥ 2 patients experience a DLT at DL -1, the dose Level -1 enrollment will be stopped and no further attempts at completing the Arm 1B of M7824 and M9241 in combination with SBRT will be conducted and Arm 2B and phase II expansion cohort of M7824 and M9241 in combination with SBRT will not be carried out.

Table 6: Dose Levels of M7824 and M9241 in combination with SBRT in Arm 1B.

Dose level	M7824, mg, IV every 2 weeks	M9241, µg/kg, SQ, every 4 weeks	SBRT
DL 0	1,200	MTD of M9241 estimated during Phase IA (16.8 or 12)	5 x 5 Gy
DL -1	1,200	If MTD estimated during Phase IA is 16.8 then 12.0	5 x 5 Gy
		If MTD estimated during Phase IA is 12.0, then 8.0	

3.1.3 Phase II, Cohort 3, Arm 2

The efficacy part of the study will be conducted with the M7824 and M9241 dose level found to be safe in combination with SBRT during phase IB. Once a recommended phase 2 dose of M7824 and M9241 has been determined, up to 25 subjects will be evaluated at that dose level, inclusive of those patients treated at the RP2D during the safety run-in.

Enrollment will start when RP2D is estimated and 28 days of observation after first treatment of 6th subject at RP2D in Arm 1B have passed.

During first stage of Phase II 16 patients will be enrolled. If 0 to 1 of 16 patients respond (PR or CR as defined in Section 6.3), then no further patients will be enrolled. If 2 or more of the first 16 evaluable patients enrolled have a response (PR or CR), then during second stage accrual will continue until a total of 25 evaluable patients have been enrolled.

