3.2 STUDY STOPPING RULES

For safety reasons, the enrollment will be temporarily halted until an expedited safety report has been evaluated by the investigators, IND sponsor, and submitted to the FDA for either of the following events attributable to treatment regimen occurring within 28 days of receiving investigational agent (s):

- One occurrence of grade 5 toxicity, attributable to treatment regimen.
- Two occurrences of grade 4 toxicity, attributable to treatment regimen.

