Grade 3 or 4 thrombocytopenia associated with bleeding	M9241 must be permanently discontinued

(CTCAEv5) Grade	Action
event which does not result in hemodynamic instability but requires an elective platelet transfusion, or a life-threatening bleeding event which results in urgent intervention and admission to an Intensive Care Unit	
Grade 4 hematologic toxicity lasting ≥ 7 days despite of medical intervention (Note: Grade 4 neutropenia lasting >5 days)	M9241 must be permanently discontinued
Cytokine release syndrome	M9241 must be permanently discontinued
* retest within 3 days from the first occurrence and then weekly to determine if ALT elevation persists	

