3.8 STUDY CALENDAR

Procedure	Screening	Baseline ¹	Day -14 ¹	Cycles (28+/- 3 days) ¹		EOT visit ^{13, 16}	28 Days FU ^{14, 16}	Long Term FU ^{15, 16}
				Day 1	Day 15			
M7824 ²			X	X	X			
M9241 ³				X				
SBRT ⁴					X (C1 only)			
Medical History	X							
Confirmation of Pathology	X							
Height	X							
Physical exam, weight, vital signs, ECOG ^{5, 17}	X	X		X	X	X	X	
Skin assessment		X		X ¹⁸			X	
EKG ¹⁷	X	X		X ⁶	X ⁶		X	
CBC with differential and platelets ¹⁷	X	X	X	X	X	X	X	
Biochemical profile ^{7, 17}	X	X	X	X	X	X	X	

Abbreviated Title: M7824, M9241 and SBRT

Version date: 11/10/2021

Procedure	Screening	Baseline ¹	Day -14 ¹	Cycles (28+/- 3 days) ¹		EOT visit ^{13, 16}	28 Days FU ^{14, 16}	Long Term FU ^{15, 16}
				Day 1	Day 15			
Pregnancy testing (urine or serum) ¹⁷	X	X		X				
A brain CT / MRI scan if clinically indicated	X							
Tumor evaluation ^{8, 17}	X	X		X (odd cycles, except C3)	X (C3 only)			X
CEA, CA19-9, CA-125 ¹⁷		X		X		X	X	
T4 and TSH ¹⁷		X		X		X	X	
Amylase / lipase ¹⁷		X		X		X	X	
Urinalysis ¹⁷		X		X		X	X	
PT, INR, aPTT, fibrinogen		X		X			X	
Concomitant Medications ¹⁷		X		X		X	X	
Baseline symptom collection		X						

Abbreviated Title: M7824, M9241 and SBRT

Version date: 11/10/2021

Procedure	Screening	Baseline ¹	Day -14 ¹	Cycles (28+/- 3 days) ¹		EOT visit ^{13, 16}	28 Days FU ^{14, 16}	Long Term FU ^{15, 16}
				Day 1	Day 15			
Collection of archival tumor sample if available for research		X						
FACT-Hep ^{9, 17}		X		X				
Adverse events ¹⁷			X	X	X	X	X	X
Research MRI ¹⁰		X		X				
Research blood for PK ¹¹			X	X	X			
Research blood for ADA sampling		X		X ¹²				
Research blood for Cytokines and TNF		X		X				
Research blood for circulating free tumor DNA (cfDNA) assay		X		X		X		
Phone call or e-mail								X

¹ Baseline and Day -14 (Arm 1A) or C1D1 (Arm 2A and Arm 3) evaluations do not need to be repeated if performed at screening or baseline in designated time frame. All evaluations will be done within 72 hours before treatment initiation on treatment days. If treatment does not start within 28 days after enrollment, screening evaluations will be repeated.

² M7824 will be administered as an IV on Days 1 and 15 of every cycle. **Note:** Additional infusion on Day -14 in Arm 1A.

³ M9241 will be administered as a subcutaneous injection on Day 1 of every cycle.

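### Asymptomatic Grade 4 neutropenia long enough to end M9241 permanently under Table 14 can still fall outside the DLT count that sets the M9241 dose

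*Combined protocol and SAP*

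**What the plan says.** Section 3.1.1 counts any Grade 3 or higher adverse event in the DLT window as a DLT unless it is on a list of exceptions. One exception is "Grade 3 or 4 clinically asymptomatic neutropenia if not lasting > 1 cycle (14 days", provided it is a laboratory finding only. The matching platelet exception is narrower: "Clinically asymptomatic grade 3 thrombocytopenia if not lasting > 1 cycle (14 days". The hemoglobin exception also stops at Grade 3.

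Table 14 (section 3.4.2) lists events after which M9241 must be stopped for good. One row reads "Grade 4 hematologic toxicity lasting ≥ 7 days despite of medical intervention (Note: Grade 4 neutropenia lasting >5 days". It makes no exception for asymptomatic or laboratory-only cases.

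Sections 3.1.2, 3.1.2.1 and 3.1.2.2 accept a dose level if fewer than 2 of 6 patients have a DLT. Tables 5 and 6 hold M7824 at 1,200 mg and lower only M9241. Section 10.4.4 uses DLTs again in the Phase II continuation rule (cumulative fraction below 1/3).

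No section makes permanent discontinuation of M9241 a DLT. The only treatment-interruption event that counts is failure to resume SBRT after a hold of at least a week, in Phase IB.

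**The concern.** The DLT count exists to decide whether the M9241 dose should come down. Under these two rules, an event severe enough that the patient may never receive M9241 again can leave that count unchanged.

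The ordering is also odd. Under section 3.1.2 a patient with a counted DLT may continue treatment at the investigator's discretion, with interruption or dose reduction. Under Table 14 a Grade 3 or 4 AST/ALT elevation that resolves allows a restart at DL -1. The exempt neutropenia allows neither. Among the hematologic exceptions it is also the only one that extends to Grade 4, and the protocol does not say why.

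At stake is the dose carried into Phase IB and then Phase II. A level could be accepted at 1 of 6 although a second patient had to stop M9241 permanently for toxicity attributed to it.

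**Working it through.** **Where the two rules overlap**

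| Duration of asymptomatic Grade 4 neutropenia | Section 3.1.1 | Table 14, neutropenia note (>5 days) | Table 14, main limit (≥7 days despite treatment) |
|---|---|---|---|
| up to 5 days | not a DLT | not triggered | not triggered |
| 6 days | not a DLT | stop M9241 | not triggered |
| 7 to 14 days | not a DLT | stop M9241 | stop M9241 |
| over 14 days | DLT | stop M9241 | stop M9241 |

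The overlap is 6 to 14 whole days under the note and 7 to 14 under the main limit. Section 3.1.1 equates one cycle with 14 days, although cycles are 28 days. Reading the limit as 28 days would widen the overlap.

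**Effect on one dose decision**

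Take one counted DLT of Grade 3 in one patient and a 10-day Grade 4 neutropenia, attributed to M9241 and persistent, in another.

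- As written: 1 of 6, and the level passes.
- With aligned limits: 2 of 6, and M9241 is reduced.
- Section 3.2 is not triggered, because only one event is Grade 4.

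With no other DLT, two such episodes would be needed to change the decision. Two attributable Grade 4 events would by then have paused enrollment.

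**How often the event might occur**

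Inputs are from section 1.2.6.1 and Table 1 (M9241 alone, 59 patients, all dose levels pooled): decreased neutrophil count was Grade 3 in 4 (4/59 = 6.8%) and Grade 4 in 0.

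- One-sided 95% upper limit for 0/59: 1 − 0.05^(1/59) = 0.0495.
- At that rate, the chance of at least one Grade 4 case in six is 1 − (1 − 0.0495)^6 = 0.263.
- The chance of two or more is 0.032.

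These figures cover Grade 4 of any duration; episodes of 6 to 14 days would be fewer. They describe M9241 alone, not the combination.

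**Effect on the chance that a level passes**

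The plan gives no operating characteristics for the six-patient rule, so there is no stated figure to reproduce. Let p be the rate of other counted DLTs and q the rate of patients whose only qualifying event is this neutropenia. Both are assumptions.

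P(pass) = (1 − r)^6 + 6r(1 − r)^5, with r = p as written and r = p + q if the episodes counted.

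| p | as written | q = 2% | q = 5% | q = 10% |
|---|---|---|---|---|
| 10% | 0.886 | 0.844 | 0.776 | 0.655 |
| 20% | 0.655 | 0.606 | 0.534 | 0.420 |

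If both levels of a run-in had the same rates (pessimistic, since the second dose is lower), the chance that both fail at p = 10% is (1 − 0.886)² = 0.013 as written. It becomes (1 − 0.844)² = 0.024 at q = 2% and (1 − 0.776)² = 0.050 at q = 5%.

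**The case against.** The strongest reply is that the rules answer different questions. Section 3.1.1 judges a dose level and Table 14 judges whether one patient is redosed. Both can be followed at once, and nothing requires every discontinuation event to be a DLT. That is correct, so this is not a contradiction in the plan. It does not explain why this particular event, in the drug being de-escalated, should be left out of the count.

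Two conditions narrow the point, and both stand. The Table 14 row refers to persistence despite treatment, and section 1.2.9.1 foresees G-CSF support. If the qualifier covers the neutropenia note, only persistent episodes end M9241. Section 3.4 also ties drug removal to attribution and requires no M9241 change for a toxicity due solely to another drug. A reader might infer that every 6-to-14-day episode ends M9241; the documents do not support that.

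A reader might also infer that an exempt episode is treated as tolerated. It is not. Sections 10.1.1, 10.4.2 and 10.4.4 report treatment-related events by number, severity and duration, and all toxicity grades in Phase I, whether or not they are DLTs.

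A third tempting reading is that the 14-day limit cannot be assessed before Phase II opens, since the scheduled Cycle 1 counts fall on Days 1 and 15 and enrollment may start once "28 days of observation after first treatment of 6th subject at RP2D in Arm 1B have passed" (section 3.1.3). A Grade 4 count first found on Day 15 reaches its fifteenth calendar day on Day 29, so the gap is only a day or two of counting. If the sample is drawn 72 hours early, as the calendar allows, the limit is crossed on Day 26 or 27. The 28 days are also a minimum. Section 6.1 already requires clinically significant laboratory abnormalities to be followed to baseline or stabilization.

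There are partial safeguards. Section 3.2 pauses enrollment after "Two occurrences of grade 4 toxicity, attributable to treatment regimen", and section 7.4.1 has the team review toxicity weekly and use it in de-escalation decisions. In Phase IB, SBRT is not started at granulocyte counts below 1,000 × 10⁶/L and is held for hematological toxicity, so the SBRT-resumption DLT may catch an episode that overlaps radiation. None of these reliably changes the DLT count. The SBRT route misses an episode that resolves before about Day 17 and does not exist in Phase IA.

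**Conclusion.** The point holds as a minor misalignment between two rules. It applies when the neutropenia is attributed to M9241 and, if the Table 14 qualifier governs, persists despite treatment. In those cases an asymptomatic Grade 4 episode of about 6 to 14 days (7 to 14 under the main limit) permanently ends M9241 but does not count toward the threshold that would lower the M9241 dose. The least protected case is one Grade 3 DLT plus one such episode, particularly in Phase IA.

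The event should be uncommon. With no Grade 4 neutropenia in 59 patients on M9241 alone, an assumed q of 2% to 5% is already generous for M9241 alone across pooled doses. At p = 10% it would lower the pass probability by 0.886 − 0.844 = 0.042 to 0.886 − 0.776 = 0.110. The rate with M7824 and SBRT is unknown, so these are illustrations over a range and not estimates. The documents do not support saying that the rules cannot both be followed, or that the RP2D is likely to be wrong.

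**What to change.** In section 3.1.1, split the neutropenia exception by grade. Keep 14 days for asymptomatic Grade 3. Exempt asymptomatic Grade 4 only if it resolves before the Table 14 discontinuation limit. In Table 14, state whether the 5-day or the 7-day limit governs neutropenia and whether the persistence-despite-treatment condition applies to it. If the sponsor intends the two rules to differ, a sentence giving the reason would serve instead.

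A timed repeat CBC after a first Grade 4 neutrophil count would make the duration easier to establish. Table 14 already sets such a schedule for ALT ("retest within 3 days from the first occurrence and then weekly to determine if ALT elevation persists"). This is an optional clarification, given section 6.1.

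The cost is wording in two places and a slightly higher chance of de-escalation, or of both levels failing and the combination being stopped. A de-escalation enrolls six more patients, within the planned maximum of 12 per run-in.
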